
Intervention: For the first 4 weeks, those in the intervention arm will receive three meals per days compliant with the Mediterranean Diet. These meals will provide approximately 1,600 kcal/day (range 1,200-2,000 kcal/day) and will be evaluated by a registered dietitian with experience with patients with cancer (e.g., [name], RD, MPH, or [name], RD) for appropriateness and nutrient adequacy. We will encourage participants to supplement the provided food with food of their choosing so as to satisfy hunger and thirst; the amount of food that is supplemented will vary greatly due to each individuals' nutrient needs, and we encourage that all food be compliant with the Mediterranean Diet. During this time participants will receive education on the principles and components of the Mediterranean Diet. This will include a phone- or computer conferencing-led education session, information packet, and cookbook, all of which were designed specifically for this study.

The questionnaires will be completed via Research Electronic Data Capture (REDCap) or via paper-and-pencil (participants' choice); the food record and daily diary will be completed on paper. They will be scored and entered into a secure database by the study team. Preliminary efficacy of the intervention on cancer-related fatigue will be assessed using the FACIT-F as a primary endpoint, and also via the BFI and symptom inventory. Adherence will be determined using the 14-Item Mediterranean Diet Assessment Tool. Blood will be collected and used immediately for real-time respiration assay on T cells, sent for analysis at UR Labs, and/or processed and stored at -80°C in the CCPL for later assays.

Specific aims:

Aim 1: to evaluate the feasibility of delivering a Mediterranean Diet intervention, as measured by adherence at both 4 weeks and 8 weeks.

*The hypothesis is that those in the Mediterranean Diet group will score higher on the 14-Item Mediterranean Diet Assessment Tool at 4 weeks and 8 weeks.*

*We will consider the feasibility of the intervention successful if >70% of participants who consent complete the study and if >70% of participants in the intervention group improve their Mediterranean Diet score at least one point from baseline to 4 weeks and baseline to 8 weeks.*

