6. Insomnia Severity Index (ISI): The Insomnia Severity Index (ISI) is a brief 7-item questionnaire that was designed to assess the severity of both nighttime and daytime components of insomnia.

Some study data (e.g., questionnaires) will be collected electronically using REDCap software. REDCap is a secure, web-based application for building and managing online surveys and databases and is made available through the CTSI. REDCap will be used to send a secured web link to each study subject, and a built-in scheduling function will allow for re-contact at a pre-specified time to remind subjects to complete the questionnaires if needed. All data forms will be checked immediately by the REDCap system as they are being completed by the study subject to ensure completeness (i.e., that no question was skipped unintentionally), and a pop-up message feature will be used to encourage a response. For participants who prefer paper-based questionnaires, a paper version will be provided for them to complete and return to the study staff in person or in a postage-paid envelope. In this case, a study staff member will enter the responses into the REDCap database.

There are a total of 11 questionnaires and survey assessments that will be completed. The on-study form will be completed at baseline only; the daily diary will be completed every day; the others will be completed at baseline, 4 weeks, and 8 weeks.

- On study (demographics and clinical characteristics; baseline only)
- FACIT-F (fatigue)

- Daily diary (single-item fatigue question)
- 14-item Mediterranean Diet assessment
- 3-day food record
- ACLS (activity)
- Symptom inventory
- BFI (fatigue)
- FACT-Cog (cognition)
- BPI (pain)
- ISI (sleep)

The daily diary will take about 10 seconds each day and the other questionnaires should take approximately 30-45 minutes total to complete.

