### *17.2 Data Handling, Rigor, Quality, and Reproducibility:*

Data will be entered in REDCap electronic forms and electronically collated in a HIPAA-compliant REDCap database managed by our Division. After collation, data will be audited electronically and visually, as needed, for errors. Appropriate graphical or statistical diagnostics methods will be employed in each of the analyses to evaluate distribution of variables (e.g., to identify shape of the distribution and outliers) and also to evaluate the model assumptions (e.g., if deviation from the statistical assumptions is found, we will use alternative methods such as transformations or nonparametric analyses). Outliers that are detected will be investigated to determine if they are due to error. If not, analyses will be conducted with and without them to assess sensitivity. Because this is a preliminary efficacy study, unless stated otherwise, all hypothesis testing will be at the two-sided 0.15 level as appropriate for screening trials. SAS, JMP, and/or R software will be used for the analyses. Following the intent-to-treat principle, all randomized survivors will be analyzed in the arm as allocated, regardless of their compliance with the intervention or Mediterranean Diet contamination in the control group.

Although participants will be randomly assigned, differences may be present between study arms on demographic or clinical variables. Study arms will be compared on baseline demographic (e.g., age), clinical (e.g., cancer diagnosis, type of chemotherapy), and behavioral (e.g., physical activity, smoking) variables. If significant imbalance is found for a variable, it will be included as a covariate in subsequent analyses following standard practice.

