### *17.4 Statistical analysis*

#### *17.4.1 Aim 1: Feasibility and adherence*

Our primary aim is to evaluate the feasibility of delivering a Mediterranean Diet patients undergoing chemotherapy. Despite us providing food to participants, we expect that there will be variability in dietary intake in the Mediterranean Diet arm due to participants not liking the taste of the meal(s), inconvenience, social barriers (e.g., eating out with friends, family, colleagues), cravings, symptoms such as nausea and diarrhea, etc. Adherence will be based on consumption of key dietary components (e.g., fruits, vegetables, olive oil, fish) and avoidance of red meat, sweet or carbonated beverages, and commercial sweets and pastries. Success will be deemed if >70% of participants who consent complete the study and if >70% of participants in the intervention arm improve their Mediterranean Diet score from pre- to post-intervention. Adherence to the provided diet will yield 13 out of 14 points on the 14-item scale (1 point for consumption of wine). The Mediterranean Diet score is commonly used in epidemiological studies to assess the relation between adherence to the Mediterranean Diet and prediabetes, metabolic syndrome, inflammation, etc. Between arm difference in Mediterranean Diet score will be evaluated by two-sample t-test.

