#### *17.4.2 Aim 2: Patient-reported fatigue*

To provide estimates of efficacy comparing the Mediterranean Diet to usual care for alleviating fatigue, we will evaluate between-arm difference in mean change in FACIT-F fatigue subscale score from baseline to 4 weeks in an ANCOVA model. The outcome will be FACIT-F fatigue score at 4 weeks with arm included as a fixed effect and FACIT-F fatigue score at baseline as a covariate. To assess the moderating effect of the baseline level of fatigue we will test arm×baseline interaction. To further evaluate the longitudinal trajectory of fatigue and the maintaining effect of the intervention, we will incorporate FACIT-F fatigue score measured at all time points (T1, T2, T3) in a repeated measures linear mixed model. The impact of patient's variables (e.g., age, gender, body mass index) on the results will be assessed by adding the covariates to the models. The results of the analyses together with the estimates of distribution parameters (e.g., mean, SD) of T1-T3 FACIT-F fatigue score values as well as the change scores will be used in planning a future randomized trial.

We expect all measures of cancer-related fatigue to increase over the course of chemotherapy, though we hypothesize that the differences will be attenuated in the intervention group. We will also compare our baseline-to-post-intervention change scores to those obtained via historical controls (e.g., [name] et al., 2018).

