#### *17.4.3 Mechanistic aims*

We will assess the preliminary efficacy of the Mediterranean Diet intervention on metabolic measures including mitochondrial function from freshly isolated T cells. We will also obtain preliminary data on effects of the Mediterranean Diet vs. usual care on established metabolic biomarkers from blood samples. In an exploratory analysis, we will use similar models as in Aim 2 to assess Mediterranean Diet score with biomarkers of metabolic function. We will use both ANCOVA models looking at data at 4 or 8 weeks adjusting for baseline values, and longitudinal models incorporating data from time points T1-T3. This battery of biomarkers will be assessed to determine which are the most useful, and which others we should include in follow-up studies. Special statistical considerations may arise and will need be addressed during the analysis of biomarkers, including the need for transformation and missing data due to the detection limits.

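### The Mediterranean Diet score is compared between arms by a two-sample t-test that names neither a baseline covariate nor the variable tested; baseline-adjusted ANCOVA at both visits would be clearer and probably somewhat more precise (minor)

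*Combined protocol and SAP*

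**What the plan says.** Section 17.4.1 gives the between-arm analysis of diet score in one sentence: "Between arm difference in Mediterranean Diet score will be evaluated by two-sample t-test". The Aim 1 hypothesis in section 4.1 is that "those in the Mediterranean Diet group will score higher on the 14-Item Mediterranean Diet Assessment Tool at 4 weeks and 8 weeks".

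The 14-item tool is given three times. Section 4.4.4 lists it among the questionnaires and says that, apart from the on-study form and the daily diary, "the others will be completed at baseline, 4 weeks, and 8 weeks"; Table 4 in section 8.2.8 agrees.

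Other outcomes are adjusted for baseline. The fatigue model in section 17.4.2 takes "FACIT-F fatigue score at baseline as a covariate". For biomarkers, section 17.4.3 says "We will use both ANCOVA models looking at data at 4 or 8 weeks adjusting for baseline values". Section 17.4.4 sends other patient-reported measures, with the BFI and FACT-Cog as examples, to methods like those of Aim 2.

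Two general rules in section 17.2 bear on the point. On covariates: "If significant imbalance is found for a variable, it will be included as a covariate in subsequent analyses following standard practice". On model assumptions: "if deviation from the statistical assumptions is found, we will use alternative methods", with transformations and nonparametric analyses as examples.

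**The concern.** The plan leaves two things open in the named test of the Aim 1 hypothesis.

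- **The variable.** The hypothesis in section 4.1 reads as a comparison of levels at 4 and 8 weeks. The success criterion in section 17.4.1, in the same paragraph as the t-test, is improvement from before to after the intervention. Either reading fits, and they give different estimates and intervals from the same data.
- **The baseline.** On the follow-up reading, a measurement already in hand is not used. The covariate rule in section 17.2 does not supply it, because it acts only after a significant imbalance. That is a data-dependent trigger, not planned adjustment for a variable expected to predict the outcome.

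At stake is the precision of the estimate of how far the intervention moved diet relative to usual care, and agreement with the rest of section 17. No decision in the trial turns on it.

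**Working it through.** **Inputs from the documents.** Evaluable N = 33, split 22:11 (section 17.1); two-sided alpha 0.15 (section 17.2), hence 85% intervals; 2:1 allocation (sections 8.2.5 and 17.1).

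**Assumed.** The correlation r between baseline and follow-up diet score, and the SDs. The 0.50 and 0.75 in section 17.1 are for FACIT-F. Excluding scores of 10 or more at entry (section 5) could lower r for the diet score.

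**Step 1. The plan's own figure.** For FACIT-F ANCOVA with r = 0.50 and effect 0.75 SD:

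- Var = (1 − 0.50²)(1/22 + 1/11) = 0.75 × 0.1364 = 0.1023, so SE = 0.320.
- 0.75/0.320 = 2.345. The normal approximation gives power Φ(2.345 − 1.440) = 0.817; the noncentral t on 30 df gives 0.806.

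The stated 80% reproduces.

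**Step 2. ANCOVA against a t-test on follow-up scores** (equal SDs, common r).

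- Variance ratio = (1 − r²)(N − 3)/(N − 4) = (1 − r²) × 30/29.
- Break-even on variance: 1 − r² = 29/30, so r = √(1/30) = 0.183.
- CI-width ratio = √(variance ratio) × t₃₀/t₃₁ = √(variance ratio) × 1.4774/1.4761. Break-even on width: r = 0.187.

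| r | variance ratio | 85% CI-width ratio |
|---|---|---|
| 0 | 1.034 | 1.018 |
| 0.2 | 0.993 | 0.997 |
| 0.3 | 0.941 | 0.971 |
| 0.5 | 0.776 | 0.882 |
| 0.7 | 0.528 | 0.727 |

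For an illustrative 0.75 SD difference and r = 0.5, power is 0.71 for the t-test and 0.80 for ANCOVA. At 1.0 SD it is 0.889 against 0.943, and at 1.5 SD 0.995 against 0.999.

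**Step 3. ANCOVA against a t-test on change.** The variance of a change score is 2(1 − r) in units of the score variance, so the ratio is (1 − r²)/[2(1 − r)] × 30/29 = (1 + r)/2 × 30/29.

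- r = 0: 0.517. r = 0.5: 0.776. r = 0.7: 0.879.
- Break-even: 1 + r = 2 × 29/30, so r = 0.933.

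**Step 4. Correlations that differ by arm** (equal SDs, follow-up t-test). The common slope is about b = (21·r_int + 10·r_con)/31, and the residual variance in each arm is 1 − 2b·r + b².

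- r = 0.4 intervention, 0 control: b = 0.271; residual variances 0.857 and 1.073; 0.857/22 + 1.073/11 = 0.1365 against 0.1364. Times 30/29 the ratio is 1.036, about 4% worse.
- r = 0.3 and 0.1: ratio 1.011, about 1% worse.
- r = 0 intervention, 0.4 control: b = 0.129; residual variances 1.017 and 0.913; ratio 0.981, about 2% better.

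The smaller arm dominates the variance, so a slope driven by the larger arm can fit it badly.

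**Step 5. Unequal spread** (simulation, 40,000 trials per setting, nominal type I error 15%). With intervention SD 0.7 or 1.4 times control, the pooled t-test rejects in about 20% or 11% of null trials, and ordinary ANCOVA in 18-19% or 10-11%. Welch holds 15% in both, and ANCOVA with HC2 standard errors and Satterthwaite degrees of freedom holds 14-15%. Section 17.4.1 does not say pooled or Welch. With HC3 errors the break-even r rises to about 0.35, because HC3 is conservative with 11 controls.

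**The case against.** **The premise is conditional.** If the t-test is on change, baseline is already used, and neither the description as unadjusted nor a threshold near 0.2 applies. This stands. It makes the undefined variable part of the defect, but does not weaken the recommendation, since ANCOVA beats a change-score test over nearly the whole range of r (step 3).

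**The threshold is not general.** A reader might infer that ANCOVA wins whenever r exceeds about 0.2. That needs a common correlation, and the cases in step 4 break it. The documents do not say in which arm the correlation would be lower.

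**Gains may be small.** This also stands. At r = 0.3 the interval narrows by about 3%. If supplied food moves scores by 1.5 SD, power is near 1 either way. "Adherence to the provided diet will yield 13 out of 14 points on the 14-item scale", and entry requires a score below 10, so large shifts are possible, but no SD is given.

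**Robust errors and a main visit would be additions of taste.** Largely accepted. Robust errors guard against unequal spread and do not produce the precision gain; the diagnostics in section 17.2 partly cover that risk. The spread could go either way: section 17.4.1 expects variable intake in the diet arm, while scores near the ceiling would compress it. Naming 4 weeks as the main visit has no basis in Aim 1, which treats both visits equally.

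**The general rule might cover it.** Section 17.4.4 could be read as extending Aim 2 methods to every questionnaire, but the specific t-test sentence in section 17.4.1 governs this score.

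**Conclusion.** The point holds as a minor matter of precision, clarity and consistency. The test leaves its variable undefined and names no baseline covariate, although the baseline is collected and most comparable outcomes in the plan are adjusted for theirs. Against a follow-up t-test the effect on the 85% interval runs from about 2% wider (r = 0) to 27% narrower (r = 0.7), assuming 22:11 evaluable, equal SDs and a common r. Whether the gain is realised depends on a correlation that the documents do not give.

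Two stronger readings are not supported. A reader might infer that the t-test gives a biased comparison; under randomisation it does not. A reader might also infer that the feasibility conclusion is at risk; it rests on two proportions above 70% (sections 4.1 and 17.4.1), and the sample size rests on FACIT-F.

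**What to change.** Replace the t-test sentence in section 17.4.1 with:

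> *Between-arm difference in Mediterranean Diet score at 4 weeks and at 8 weeks will be estimated by ANCOVA with arm as a fixed effect and baseline Mediterranean Diet score as covariate, reported with confidence intervals.*

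This settles the variable and the visits and matches the Aim 2 model. No main visit needs naming. Heteroscedasticity-robust standard errors are an option if spread differs by arm under 2:1 allocation; if used, state the type (HC2, for example), since HC3 would give up much of the gain.

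The cost is one sentence, with no new data, visits or patients. The downside is a variance about 3% larger if baseline does not predict follow-up, or about 4% larger in the unequal-correlation case shown (0.4 against 0).

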#### *17.4.2 Aim 2: Patient-reported fatigue*

To provide estimates of efficacy comparing the Mediterranean Diet to usual care for alleviating fatigue, we will evaluate between-arm difference in mean change in FACIT-F fatigue subscale score from baseline to 4 weeks in an ANCOVA model. The outcome will be FACIT-F fatigue score at 4 weeks with arm included as a fixed effect and FACIT-F fatigue score at baseline as a covariate. To assess the moderating effect of the baseline level of fatigue we will test arm×baseline interaction. To further evaluate the longitudinal trajectory of fatigue and the maintaining effect of the intervention, we will incorporate FACIT-F fatigue score measured at all time points (T1, T2, T3) in a repeated measures linear mixed model. The impact of patient's variables (e.g., age, gender, body mass index) on the results will be assessed by adding the covariates to the models. The results of the analyses together with the estimates of distribution parameters (e.g., mean, SD) of T1-T3 FACIT-F fatigue score values as well as the change scores will be used in planning a future randomized trial.

We expect all measures of cancer-related fatigue to increase over the course of chemotherapy, though we hypothesize that the differences will be attenuated in the intervention group. We will also compare our baseline-to-post-intervention change scores to those obtained via historical controls (e.g., [name] et al., 2018).

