#### 4.3 Study interventions

Participants will be randomly assigned 2:1 to a Mediterranean Diet or usual care using a computer-generated random numbers table with blocks of 3 or 6. Patients will be stratified based on how frequently their chemotherapy is planned to be administered. One strata will include patients who plan to receive

[figure not shown]
weekly, biweekly (Q2w), or every 4-week (Q4w) regimens, and the other strata will include those on other regimens (e.g., Q3w). This stratification will allow us to account for who is at the “end” of a cycle and who is in the “middle” of a cycle at the 4- and 8-week assessment points.

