#### 4.4.4 Exploratory aims and other symptoms and clinical factors

In order to assess the variation in fatigue over the course of a chemotherapy cycle, we will assess average fatigue at the end of each day using a single-item question on a daily diary.

To obtain more precise estimates on the effects of the Mediterranean Diet on cancer-related fatigue and metabolism we will account for several behavioral and clinical factors. For example, several patient-reported outcomes tend to be associated with fatigue (e.g., depression) and we will adjust for these potential factors in our analyses.

1. Aerobics Center Longitudinal Study (ACLS) physical activity questionnaire: The ACLS captures current physical activity and exercise, including walking, climbing stairs, and weight training. We will use this questionnaire to estimate the energy that each participant expends per week on physical activity.
2. Symptom Inventory (SI): The symptom inventory (modified from the MD Anderson Symptom Inventory) includes 19 items that are common in the cancer experience (e.g., pain, distress, lack of appetite, numbness and tingling, fatigue), as well as 8 items related to how much these symptoms interfere with activities of daily living and quality of life. As many symptoms often correlate with each other including fatigue (i.e., symptom clustering), it is important to capture the change in many symptoms from baseline to post-intervention. Exploratory analyses will probe whether adherence to the diet or high consumption of any dietary component correlates with the change in any of these symptoms over time.
3. Brief Fatigue Inventory (BFI): The BFI is a 10-item fatigue questionnaire that is also validated and commonly used. It captures fatigue *now* as well as the usual and worst in the last 24 h. It also includes 6 single-item questions regarding how fatigue has interfered with general activity, mood, work, etc.
4. FACT-Cog: The FACT-Cog is a 41-item questionnaire designed to assess cognitive challenges identified by patients with cancer.
5. Brief Pain Inventory: The Brief Pain Inventory (BPI)-Short Form is a 15-item questionnaire designed to assess the severity of pain and its impact on functioning.

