#### *8.2.5 Randomization procedures*

Randomization will be revealed to the participant at the end of the baseline assessments, before delivering the instructional portion of the intervention.

We will employ two treatment arms in a 2:1 allocation ratio:

1. Mediterranean Diet: an 8-week intervention entailing education of the Mediterranean Diet and delivery of Mediterranean Diet-inspired meals for 4 weeks.
2. Usual care: completion of assessments, with no intervention and usual care for their cancer.

Consented subjects will be randomized with a computer-generated random numbers table with block sizes of 3 and 6 and stratified based on how frequently they will be receiving chemotherapy (weekly, biweekly, or every 4 weeks vs. other). The random numbers tables will be generated centrally by [name], the project biostatistician, or a designee. A total enrollment of 42 subjects is planned.

Participants cannot be blinded due to the nature of the intervention. PI blinding is also not feasible given that the PI will play an active role in recruitment, intervention delivery, data acquisition, and analysis.

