## 17. Data analysis plan

### 17.1 Sample size determination

This is a two-arm randomized controlled trial that will assess feasibility of delivering a Mediterranean Diet intervention to patients undergoing chemotherapy, as well as the preliminary efficacy of a Mediterranean Diet intervention vs. usual care on the prevention of cancer-related fatigue. Our sample size is based on our fatigue outcome as measured using the FACIT-F fatigue subscale, which is a 13-item scale with responses that range from 0-4; the FACIT-F subscale score ranges from 0-52 and a higher score indicates greater wellbeing and less fatigue. The minimal clinically important difference for the FACIT-F is 3 points.

We plan to recruit a total of 42 participants and randomize them in a 2:1 ratio, intervention: control (28:14) using computer-generated block randomization with blocks of 3 or 6. Patients will be stratified based on how frequently their chemotherapy is planned to be administered. One strata will include patients who plan to receive weekly, biweekly (Q2w), or every 4-week (Q4w) regimens, and the other strata will include those on other regimens (e.g., Q3w). Thus, those in the first strata will complete 4-week and 8-week assessments for our study at the end of a chemotherapy cycle, while those in the second strata will be completing assessments in the middle of their cycle. (If there are

**Fig. 3.** Effect size vs. sample size at 70% and 80% power with 33 participants on the study.

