dose delays or changes to the chemotherapy schedule, we will still collect assessments at the originally planned time.) We estimate attrition between approximately 20 and 25%, thus we estimate to retain 33 (22:11) evaluable patients. This sample size is appropriate for small randomized pilot studies and it will allow us to obtain preliminary estimates of descriptive statistics [mean, standard deviation (SD), and confidence intervals (CI)]. The primary endpoint is the change in fatigue as measured by FACIT-F from baseline (T1) to 4 weeks (T2). Assuming a correlation of 0.50 between T1 and T2 FACIT-F measurements, a total sample size of n=33 will provide 80% power at the 0.15 two-sided significance level to detect an effect size (ES, standardized mean between-group difference) of 0.75 of the intervention effect on change in T2-T1 FACIT-F using analysis of covariance (ANCOVA) with T1 FACIT-F as a covariate (**Fig. 3**). The estimates of T1-T2 correlation and attrition rate are based on our prior studies.

Feasibility is often determined for nutrition interventions among 10-15 participants (e.g.,); pilot preliminary efficacy studies usually recruit 20-30 (e.g.,). **Table 6** below shows prior studies that are similar to this one, including their sample size.

Study	n	Population	Intervention	Outcome	Results
Zick et al. (2017) 	30	breast cancer survivors	Fatigue reduction diet vs. General Health Curriculum (time and attention control) for 3 months	Brief Fatigue Inventory	From baseline to 3-months, fatigue improved by 44±39% in diet group compared to 8±34% in the control group (p=0.01)
Skouroliakou et al. (2018) 	70	breast cancer survivors	Mediterranean Diet for 6 months vs. handout	serum antioxidant capacity and body composition	The dietary intervention based on Mediterranean Diet improved serum antioxidant capacity, body composition, and glycemic profile.
McMillan et al. (2011) 	27	healthy women in their 20's	Mediterranean Diet vs. control for 10 days	Profile of Mood States	A group × time interaction demonstrated that the Mediterranean Diet reduced fatigue (p=0.16) and improved vigor (p<0.01).

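### The primary ANCOVA does not name the randomisation stratum (chemotherapy frequency); if the stratum predicts week-4 fatigue, the standard error is somewhat too large and the 0.15-level test slightly conservative

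*Combined protocol and SAP*

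**What the plan says.** **Randomisation.** Section 8.2.5 has patients "stratified based on how frequently they will be receiving chemotherapy", in two levels (weekly, every 2 weeks or every 4 weeks, against other), 2:1 in blocks of 3 and 6. Section 4.3 gives an analytic purpose: "This stratification will allow us to account for who is at the" end, and who is in the middle, of a cycle at the 4- and 8-week assessments. Section 17.1 repeats it: "those in the first strata will complete 4-week and 8-week assessments for our study at the end of a chemotherapy cycle", and the other stratum mid-cycle.

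**Primary model.** In section 17.4.2 the outcome is "FACIT-F fatigue score at 4 weeks with arm included as a fixed effect and FACIT-F fatigue score at baseline as a covariate". The power statement in section 17.1 rests on the same model, "using analysis of covariance (ANCOVA) with T1 FACIT-F as a covariate". Neither names the stratum.

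**Text that could admit the stratum.**
- Section 4.4.4 says of the diet's effects that "we will account for several behavioral and clinical factors" and, of correlates of fatigue such as depression, "we will adjust for these potential factors in our analyses".
- Section 17.2 adds a baseline variable as a covariate if a significant imbalance between arms is found.
- Section 17.4.2 will examine the impact of patient variables, with age, gender and body mass index as examples.

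**Other models.** Section 17.4.2 does not list the fixed effects of the T1-T3 mixed model. Sections 17.4.3 (biomarkers) and 17.4.4 (other questionnaires) reuse the Aim 2 approach.

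**The concern.** Stratified blocks hold the arms nearly balanced on the stratum, so differences between strata largely drop out of the arm comparison. A model without the stratum leaves those differences in its residual variance. It then reports more uncertainty than the design produces: the interval is too wide and the test rejects less often than 15% under the null.

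The plan states a reason to account for cycle position, and its primary model does not do so. The permissive text does not close the gap. The imbalance rule in 17.2 is unlikely to bring in a variable that the blocks keep balanced, and the covariates in 17.4.2 serve to examine the result, not to define the primary model. Section 8.2.5 has the principal investigator, unblinded, taking part in the analysis, which is a further reason to settle the terms in advance. Section 17.4.2 says the estimates will feed the design of a later trial, so a correct standard error is one of this pilot's products.

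**Working it through.** **1. The plan's own figure.** Inputs from 17.1: 22 and 11 evaluable patients, effect size 0.75, baseline to week-4 correlation 0.50, two-sided alpha 0.15. In SD units of the score:
- residual SD after baseline = √(1 − 0.5²) = 0.866
- SE = 0.866 × √(1/22 + 1/11) = 0.866 × 0.3693 = 0.320
- power ≈ Φ(0.75/0.320 − 1.440) = Φ(0.906) = 81.7%; with the noncentral t on 30 df, 80.6%

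The stated 80% is reproduced.

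**2. What leaving out the stratum does.** Let the strata be equal in size and differ by *g* SD at week 4, on top of the planned SD.
- Residual variance without the stratum = 0.75 + 0.25*g*²; with it, 0.75.
- At *g* = 0.5: reported SE = √(0.8125 × 0.1364) = 0.333 against 0.320, a ratio of 1.041. With perfect balance, type I error = 2 × [1 − Φ(1.440 × 1.041)] = 13.4%.
- At *g* = 1.0: SE = √(1.0 × 0.1364) = 0.369, a ratio of 1.155. Type I error = 2 × [1 − Φ(1.440 × 1.155)] = 9.6%.

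Dropout and incomplete blocks loosen the balance, so simulation is the better guide.

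**3. Simulation.** 20,000 trials per setting: 42 patients, 2:1 in blocks of 3 or 6 within two strata, about 9 lost at random, correlation 0.5, alpha 0.15, effect size 0 or 0.75. Monte Carlo error on power is about 0.6 point. The documents give neither the gap nor the split between strata; both are assumed.

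Gap on top of the planned SD, equal strata:

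| Gap (SD) | Mean SE without | True SD without | Type I error without | Power without | Power with |
|---|---|---|---|---|---|
| 0 | 0.325 | 0.328 | 15.3% | 79.4% | 78.9% |
| 0.25 | 0.328 | 0.331 | 15.0% | 78.6% | 78.8% |
| 0.5 | 0.337 | 0.332 | 14.0% | 77.2% | 78.6% |
| 0.75 | 0.354 | 0.336 | 12.5% | 75.3% | 79.4% |
| 1.0 | 0.376 | 0.345 | 11.4% | 71.4% | 79.3% |

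With the stratum in the model, type I error is 14.9 to 15.3% throughout. A 70:30 split is similar (at 1.0 SD: type I error 12.0%, power 72.6% without and 78.8% with).

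Gap inside the planned SD, equal strata:

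| Gap (SD) | Type I error without | Power without | Power with |
|---|---|---|---|
| 0.25 | 14.6% | 79.7% | 80.1% |
| 0.5 | 13.6% | 80.0% | 81.9% |
| 0.75 | 12.2% | 80.6% | 85.1% |
| 1.0 | 9.6% | 82.0% | 90.4% |

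**4. How much is real precision.** In the inside setting at 0.5 SD, the reported half-width falls by 3.9% when the stratum is added, but the true SD of the estimate falls by only about 0.8%. The rest corrects an overstated SE.

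**5. How large a gap is plausible.** In the inside setting with equal strata, the stratum would have to explain *g*² × 0.25/0.75 of the variance left after baseline: 8% at 0.5 SD, 19% at 0.75 and 33% at 1.0. A gap of 0.75 SD would equal the treatment effect the trial is sized for. Table 3 in 8.2.7 argues against so large a gap. Weekly and every-3-week patients, in opposite strata, both have a week-4 infusion. The first stratum itself mixes weekly patients with every-2-week patients (last infused in week 3) and every-4-week patients (week 1).

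**The case against.** The strongest reply is that this is a matter of wording with almost no consequence. The plan does not exclude the stratum, and the error runs in the safe direction. The trial is a screening pilot tested at the 0.15 level whose stated primary aim is feasibility. The stratum also separates cycle position poorly. Besides the overlap in Table 3, section 8.2.7 aims for assessments at least 3 days after an infusion and lets the 4-week visit fall in weeks 3 to 5. Under dose delays, section 17.1 says "we will still collect assessments at the originally planned time". Most of this stands. It is why only the rows up to 0.5 SD should be read as realistic. It does not remove the point, because permission to add a term is not a statement that the primary model contains it.

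A reader might infer more than the documents support:
- *That the 80% power statement is wrong, or that it is safe whatever the stratum does.* Neither follows. The documents give no SD for the score and do not say whether the planning SD contains the stratum gap.
- *That the mixed model omits the stratum, or must carry a stratum-by-visit term.* Section 17.4.2 lists no fixed effects for that model, so no omission can be shown. The argument for stratum-by-visit relies on a baseline taken before the first infusion, and 8.2.7 permits one after chemotherapy has started.

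**Conclusion.** The point holds as a free improvement. The stratum is used to randomise and is absent from the stated primary model. If it predicts week-4 fatigue beyond baseline, the reported SE is somewhat too large and the test slightly conservative. The estimate is unbiased and type I error is not inflated.

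The size depends on an assumed gap:
- **0.25 SD or less:** nil in practice.
- **0.5 SD:** type I error about 13.5 to 14% instead of 15%, and about 1 to 2 points of power lost.
- **0.75 to 1.0 SD:** upper bounds, with type I error roughly 10 to 12.5% with equal strata and about 3 to 8 points of power lost.

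The 80% in 17.1 holds without the stratum if the planning SD already includes the gap. If the gap lies on top, power without the stratum is about 77% at 0.5 SD and 71% at 1.0 SD, and including it restores about 78 to 79%. These figures rest on the planned correlation, random dropout and the assumed strata sizes.

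**What to change.** In 17.4.2, state the primary model as: week-4 FACIT-F fatigue score = arm + baseline FACIT-F fatigue score + randomisation stratum (as randomised). Use the same term in the ANCOVAs of 17.4.3 and 17.4.4 that follow the Aim 2 method. When the fixed effects of the T1-T3 mixed model are written, include the stratum there too; letting its effect differ by visit is an option, not a required correction.

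In 17.1, one sentence could say whether the planning SD includes variation between strata. The sample size need not change.

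The cost is 1 df in the ANCOVA and about 0.5 point of power if the stratum has no effect. The variable is already in the randomisation list, so nothing new has to be collected.
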